10.5 Cycle 2 Day 1 (+/- 3 days)

10.5.1 MD visit, with history and physical examination, including weight, blood pressure, pulse, ECOG performance status, patient drug diary review, and updated medication list. Concurrent medications will be reviewed for potential drug-drug interactions with study medication (see Section 9.6).

10.5.2 Toxicity will be assessed and the type, severity, timing, and relationship of each adverse event to therapy will be determined as per the NCI Common Toxicity Criteria, version 4.0.

10.5.3 Fasting bloodwork prior to taking BYL719 in clinic on this day. A light breakfast may be consumed after fasting plasma glucose draw. BYL719 may be administered 1 hour after breakfast. Patients should fast for 1 hour after the administration of BYL719. Bloodwork results do not need to be resulted prior to dosing on this day (because BYL719 dosing is continuous); however, all bloodwork must be reviewed and the patient contacted within 24 hours (excluding weekends and holidays) if an abnormality is detected which would affect dosing.

- CBC, including WBC (differential not required), Hgb and platelet count
- CMP, including BUN, creatinine and liver function tests
- Magnesium, amylase and lipase
- Fasting glucose
- Tumor markers (CA 15-3 and CEA)
- Plasma collection from 10 ml blood for cfDNA extraction and analysis

10.5.4 EKG will be performed and reviewed prior to dosing.

10.5.5 PK bloodwork for research purposes (see schedule in Section 10.11).

10.6 Cycle 2 Day 15 (+/- 3 days)

10.6.1 MD visit, with history and physical examination, including weight, blood pressure, pulse, ECOG performance status, and patient drug diary review.

10.6.2 Toxicity will be assessed and the type, severity, timing, and relationship of each adverse event to therapy will be determined as per the NCI Common Toxicity Criteria, version 4.0.

10.6.3 Fasting bloodwork prior to taking BYL719 in clinic on this day. A light breakfast may be consumed after fasting plasma glucose draw. BYL719 may be administered 1 hour after breakfast. Patients should fast for 1 hour after the administration of BYL719. Bloodwork results do not need to be resulted prior to dosing on this day

(because BYL719 dosing is continuous); however, all bloodwork must be reviewed and the patient contacted within 24 hours (excluding weekends and holidays) if an abnormality is detected which would affect dosing.

- CBC, including WBC (differential not required), Hgb and platelet count
- CMP, including BUN, creatinine and liver function tests
- Magnesium, amylase and lipase
- Fasting glucose

10.6.4 EKG will be performed and reviewed prior to dosing.

10.6.5 PK bloodwork for research purposes (see schedule in Section 10.11).

10.7 Subsequent Cycles (Cycle 3+) Day 1 (+/- 7 days)

10.7.1 One MD clinic visit per cycle, with history and physical examination, including weight, blood pressure, pulse, ECOG performance status, patient drug diary review, and updated medication list. Concurrent medications will be reviewed for potential drug-drug interactions with study medication (see Section 9.6).

10.7.2 Toxicity will be assessed and the type, severity, timing, and relationship of each adverse event to therapy will be determined as per the NCI Common Toxicity Criteria, version 4.0.

10.7.3 Fasting bloodwork prior to taking BYL719 in clinic on this day. A light breakfast may be consumed after fasting plasma glucose draw. BYL719 may be administered 1 hour after breakfast. Patients should fast for 1 hour after the administration of BYL719. Bloodwork results do not need to be resulted prior to dosing on this day (because BYL719 dosing is continuous); however, all bloodwork must be reviewed and the patient contacted within 24 hours (excluding weekends and holidays) if an abnormality is detected which would affect dosing.

- CBC, including WBC (differential not required), Hgb and platelet count
- CMP, including BUN, creatinine and liver function tests
- Magnesium, amylase and lipase
- Fasting glucose
- Tumor markers (CA 15-3 and CEA)
- Plasma collection from 10 ml blood for cfDNA extraction and analysis

10.7.4 EKG will be performed and reviewed on Day 1 +/- 7 days of Cycle 3, Cycle 5, and then every 3rd cycle (Cycle 8, Cycle 11, etc).

10.7.5 PK bloodwork for research purposes (for specified cycles only, see schedule in Section 10.11).

10.7.6 Estradiol will be performed Day 1 +/- 7 days of Cycle 3, Cycle 5, and then every 3rd cycle (Cycle 8, Cycle 11, etc) thereafter, for patients who are receiving pharmacologic ovarian suppression

10.7.7 **Patients who are on study under Amendment 13** will present for one MD visit every other cycle. Patient's will complete all assessments per Section 10.1.

10.8 End of Treatment (within 28 days of last dose of BYL719)

10.8.1 MD visit, with history and physical examination, including weight, blood pressure, pulse, ECOG performance status, and final patient drug diary review.

10.8.2 Toxicity will be assessed and the type, severity, timing, and relationship of each adverse event to therapy will be determined as per the NCI Common Toxicity Criteria, version 4.0.

10.8.3 Fasting bloodwork (if not already performed in the last 28 days).

- CBC, including WBC (differential not required), Hgb and platelet count
- CMP, including BUN, creatinine and liver function tests
- Magnesium, amylase and lipase
- Fasting glucose
- Tumor markers (CA 15-3 and CEA)
- Plasma collection from 10 ml blood for cfDNA extraction and analysis

10.8.4 EKG will be performed (if not already performed in the last 28 days).

10.8.5 All patients may be asked to undergo an optional tumor biopsy at progression, with the exact timing to be at the discretion of the investigator and patient (not necessarily within 28 days of last dose of BYL719), although a 2 week window is allowed.

10.9 Evidence of Disease (EOD) Evaluation

Patients on all study arms will have an evidence of disease (EOD) evaluation at baseline, consisting of CT of chest/abdomen +/- pelvis (with oral and IV contrast unless contraindicated) and a bone scan. Patients will then have EOD evaluation with CT of chest/abdomen +/- pelvis every two cycles (8 weeks) for the first four cycles (16 weeks) of study treatment (Day 1 +/- 7 days of Cycle 3 and Cycle 5), and then every 3rd cycle (12 weeks) thereafter (Day 1 +/- 7 days of Cycle 8, Cycle 11, etc). EOD evaluation will occur every 16 weeks +/- 4 weeks from the last evaluation for patients who are on study under Amendment 13. EOD evaluation will also be performed at the end of study treatment, if not already performed in the last 28 days. A bone scan may also be performed per investigator discretion. In patients without bone-only disease, bone scans may be repeated in the event of clinical suspicion of progression of existing bone lesions, the development of new bone lesions, and in the assessment of a complete response, if any disease was evident at screening. For patients with locally-advanced unresectable breast cancer, radiographic assessments using MRI scans are acceptable to evaluate response, and a CT scan of chest/abdomen is not required.

It remains to be determined whether FDG-PET response accurately predicts tumor response to PI3K/AKT pathway inhibitors. Glucose metabolism is regulated through PI3K/AKT signaling. Inhibition of the PI3K/AKT pathway therefore inhibits glucose uptake on FDG-PET. Although FDG-PET may be a pharmacodynamic marker of pathway inhibition, clinical correlation with tumor response has not been confirmed. Therefore, CT imaging (+/- bone scan) is the preferred approach at this time.

RECIST criteria version 1.1 will be used to evaluate therapeutic response. With the development of progressive disease, patients will be removed from the study. For equivocal findings of progression (e.g., very small and uncertain new lesions, cystic changes or necrosis in existing lesions, or other such equivocal findings), treatment may continue until the next scheduled assessment at the discretion of the treating physician. If, at the next scheduled assessment, progression is confirmed, the date of progression should be the earlier date when progression was suspected.

10.10 Toxicity Management

Investigators will assess the occurrence of AEs and SAEs at all patient evaluation time points during the study. All AEs and SAEs whether volunteered by the patient, discovered by the study personnel during questioning, or detected through physical examination, laboratory test, or other means will be recorded in the patient's medical history and on the appropriate AE or SAE CRDB page. Each recorded AE or SAE will be described by its duration (i.e., start and end dates), severity, and suspected relationship to the protocol treatment. Since this trial's primary outcome is to measure safety and feasibility of the intervention by assessing toxicity to determine the MTD by measuring experiences of DLT, suspected relationships or attributions of adverse events will only be collected if assessed as grade ≥ 2 . Additionally all laboratory toxicities will be collected for assessment if the results are considered grades ≥ 2 .

Toxicity will be assessed using the NCI Common Toxicity Criteria, version 4.0, unless otherwise specified. The type, severity, timing and relationship of each adverse event will be documented. Criteria for defining dose-limiting toxicities (DLTs) are defined in Section 9.3. Criteria for defining serious adverse events (SAEs) are defined in Section 17.2.

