9.4 Dose-Limiting Toxicity (DLT) Definition

Toxicity will be tabulated using the NCI Common Toxicity Criteria (CTCAE), version 4.0. A dose-limiting toxicity (DLT) is defined as an adverse event or abnormal laboratory value assessed as at least possibly related to the study medication, meeting any of the criteria listed in the table below, and occurring during Cycle 1 (≤ 28 days following the first dose of BYL719, including those in which the event started in Cycle 1 and the confirmation of the DLT occurs in a subsequent cycle). Whenever a patient experiences toxicity that fulfills the criteria for a DLT, treatment with the study drug will be interrupted and the toxicity will be followed up (see toxicity management guidelines in Section 10).

As an additional safety measure to assess for late-appearing toxicity, a confirmatory safety assessment will be performed at the end of Cycle 2. If dose-limiting toxicity is observed between 28 days and 56 days, then safety data will be reviewed by the Principle Investigator and Novartis, and this information will inform the dose-finding cohorts.

Table 9-2 Dose-Limiting Toxicity Criteria

Toxicity	DLT criteria
Blood and lymphatic system disorders	Anemia CTCAE Grade 3 for > 14 consecutive days
	Anemia CTCAE Grade 4
	Febrile neutropenia CTCAE Grade ≥ 3
	Neutropenia CTCAE Grade 3 for > 7 consecutive days
	Neutropenia CTCAE Grade 4
	Thrombocytopenia CTCAE Grade 3 for > 7 consecutive days and/or with signs of clinically significant bleeding
	Thrombocytopenia CTCAE Grade 4
Cardiac disorders	Cardiac toxicity CTCAE Grade ≥ 3 or cardiac event that is symptomatic or requires medical intervention
	Clinical signs of cardiac disease, such as unstable angina or myocardial infarction, or Troponin CTCAE Grade 3 (confirmed with a repeat Troponin within 24 hrs)
	ECG QTc interval prolonged CTCAE Grade ≥ 3
Vascular disorders/ Hypertension	Persistent hypertension CTCAE Grade ≥ 3 requiring more than one drug or more intensive therapy than previously
General disorders and administration site conditions	Fatigue CTCAE Grade 3 for > 7 consecutive days
Skin and subcutaneous tissue disorders ^a : Rash and/or photosensitivity	Rash or photosensitivity CTCAE Grade 3 for >7 consecutive days despite skin toxicity treatment, or any second or third occurrence of CTCAE Grade 3 rash regardless of duration
	Rash or photosensitivity CTCAE Grade 4

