Metabolism and nutrition disorders: Hyperglycemia ^b	Hyperglycemia Grade 3(fasting plasma glucose 250 – 500mg/dL) (confirmed with a repeat fasting plasma glucose test within 48 hours) that does not resolve to grade 0 within 14 consecutive days (after initiation of oral anti-diabetic treatment)
	Hyperglycemia Grade 4
	Hyperglycemia leading to diabetic keto-acidosis, hospitalization for IV insulin infusion, or non-ketotic coma
GI disorders ^a	Diarrhea CTCAE Grade ≥ 3 for ≥ 48 hrs, despite the use of anti-diarrhea therapy
	Nausea/vomiting CTCAE Grade ≥ 3 for ≥ 48 hrs, despite the use of anti-emetic therapy
	Pancreatitis CTCAE Grade ≥ 3
Eye disorder	CTCAE Grade ≥ 3

Toxicity	DLT criteria
Blood chemistries ^c	Blood bilirubin ^d CTCAE Grade 2 for > 7 consecutive days
	Blood bilirubin ^d CTCAE Grade ≥ 3
	AST or ALT CTCAE Grade ≥ 3 in conjunction with blood bilirubin ^d CTCAE Grade ≥ 2 of any duration
	AST or ALT CTCAE Grade 3 for > 7 consecutive days
	AST or ALT CTCAE Grade 4
	Serum alkaline phosphatase CTCAE Grade 4
	Serum lipase and/or serum amylase (asymptomatic) CTCAE Grade 3 for > 7 consecutive days
	Serum lipase and/or serum amylase (asymptomatic) CTCAE Grade 4
	Serum creatinine CTCAE Grade 2 for > 7 consecutive days
	Serum creatinine CTCAE Grade ≥ 3
Other hematologic and non-hematologic toxicities	Any other clinically significant CTCAE ≥ Grade 3 toxicity
	Any intolerable CTCAE Grade 2 toxicity
	Apart from the criteria listed above, if a lower grade AE leads to a dose interruption of more than 7 consecutive days of BYL719, this AE will be considered as DLT

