	
days of last dose of BYL719), although a 2 week window is allowed.
 
c Companion normal DNA for targeted gene sequencing analysis (1ml whole blood for correlative science, Section 10.12)
 
d Day 1 +/- 7 days of Cycle 3, Cycle 5, and then every 3rd cycle (Cycle 8, Cycle 11, etc)
 
e If EOD not already performed in the last 28 days
 
f Cycle 3, Cycle 4, Cycle 5, Cycle 6, Cycle 8 and Cycle 10 for letrozole arm (Arm A) and Cycle 3 only for exemestane arm (Arm B)
 
g Estradiol to be tested only on women who are receiving pharmacologic ovarian suppression
 
h Patients on study under Amendment 13 will have relevant blood and cfDNA collection every other cycle (+/- 7 days).
 
i Patients on study under Amendment 13 will have EOD evaluations will be preformed every 16 weeks +/- 4 weeks from their last scan.
 
j Patients on study under Amendment 13 will have EKG evaluations every 4 cycles. EKG evaluations may be preformed more frequently at the discretion of the MD.

--	---

10.2 Cycle 1 Day 1

- 10.2.1 MD visit, with history and physical examination, including weight, blood pressure, pulse, ECOG performance status, and updated medication list. Concurrent medications will be reviewed for potential drug-drug interactions with study medication (see Section 9.6).
- 10.2.2 Toxicity will be assessed and the type, severity, timing, and relationship of each adverse event to therapy will be determined as per the NCI Common Toxicity Criteria, version 4.0.
- 10.2.3 Fasting bloodwork prior to taking BYL719 in clinic on this day (if screening bloodwork was not performed within 72 hours of dosing). A light breakfast may be consumed after fasting plasma glucose draw. BYL719 may be administered 1 hour after breakfast. Patients should fast for 1 hour after the administration of BYL719. Bloodwork results do not need to be resulted prior to dosing on this day; however, all bloodwork must be reviewed and the patient contacted within 24 hours (excluding weekends and holidays) if an abnormality is detected which would affect dosing. If a patient is being screened and starting treatment on the same day, then results of CBC, CMP and fasting glucose must be reviewed prior to enrollment and initiation of treatment.
- CBC, including WBC (differential not required), Hgb and platelet count
 - CMP, including BUN, creatinine and liver function tests
 - Magnesium, amylase and lipase
 - Fasting glucose
 - PT/INR and PTT

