17.3 Serious Adverse Event (SAE) Reporting

An adverse event is any undesirable sign, symptom or medical condition occurring after starting study drug (BYL719), even if the event is not considered to be related to study drug. Information about all adverse events, whether volunteered by the subject, discovered by investigator questioning, or detected through physical examination, laboratory test or other means, will be collected, recorded and followed as appropriate. Medical conditions/diseases present before starting study treatment are only considered adverse events if they worsen after starting study treatment (any procedures specified in the protocol). Adverse events occurring before starting study treatment but after signing the informed consent form are recorded. Abnormal laboratory values or test results constitute adverse events only if they induce clinical signs or symptoms or require therapy, and are recorded.

A serious adverse event (SAE) is an undesirable sign, symptom or medical condition which:

1. is fatal or life-threatening,
2. required or prolonged hospitalization,
3. results in persistent or significant disability/incapacity,
4. constitutes a congenital anomaly or a birth defect, or
5. is medically significant, may jeopardize the subject and may require medical or surgical intervention to prevent one of the outcomes listed above.

Events not considered to be serious adverse events are hospitalizations for:

- routine treatment or monitoring of the studied indication, not associated with any deterioration in condition,
- treatment, which was elective or pre-planned, for a pre-existing condition that did not worsen,
- treatment on an emergency, outpatient basis for an event not fulfilling any of the definitions of serious given above and not resulting in hospital admission.

Any serious adverse event occurring after the patient has provided informed consent, has started taking the study medication, and until 30 days after the patient has stopped study participation must be reported. This includes the period in which the study protocol interferes with the standard medical treatment given to a patient (e.g. treatment withdrawal during washout period, change in treatment to a fixed dose of concomitant medication). The period after discontinuing study drug may be extended if there is a strong suspicion that the drug has not yet been eliminated.

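### Section 10.10 limits attribution to grade 2 and above, against its own text and against one lower-grade row of the DLT table

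*Combined protocol and SAP*

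**What the plan says.** On attribution, Section 10.10 makes three statements:

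- "Each recorded AE or SAE will be described by its duration (i.e., start and end dates), severity, and suspected relationship to the protocol treatment".
- Because the trial measures DLTs, "suspected relationships or attributions of adverse events will only be collected if assessed as grade" 2 or higher.
- "The type, severity, timing and relationship of each adverse event will be documented".

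The visit sections side with the first and third. Section 10.2.2 says that the "relationship of each adverse event to therapy will be determined as per the NCI Common Toxicity Criteria", and Sections 10.4.2 to 10.8.2 repeat this.

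Section 9.4 defines a DLT as an adverse event or abnormal laboratory value that is "assessed as at least possibly related to the study medication", meets a criterion of Table 9-2 and occurs in Cycle 1. The last row of that table adds that "if a lower grade AE leads to a dose interruption of more than 7 consecutive days of BYL719, this AE will be considered as DLT".

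On laboratory values, Section 10.10 collects all laboratory toxicities of grade 2 or higher. Section 17.3 says: "Abnormal laboratory values or test results constitute adverse events only if they induce clinical signs or symptoms or require therapy, and are recorded". The global stopping rule in Sections 9.6 and 14.3 counts patients with a grade 4 toxicity.

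**The concern.** The attribution limit is justified by the need to measure DLTs, yet it leaves out information that one DLT criterion requires. If the database follows the limiting sentence, a grade 1 event that keeps a patient off BYL719 for more than 7 days has no recorded relationship. It then cannot be shown either to be a DLT or not to be one.

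The count matters because the cohorts are small. Under Section 9.5, at Cohorts 0 and +1, one DLT in the first three patients turns escalation into adding up to three more patients. At every level, a second DLT among six turns acceptance into rejection. The recommended dose declared for Arm D is the Cohort +2 level, so it rests on no more than one DLT in six.

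The laboratory wording raises a smaller question. Section 10.10 collects an untreated, asymptomatic grade 4 value, but under Section 17.3 that value is not an adverse event. The stopping rule does not say which convention applies.

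**Working it through.** **1. The attribution statements side by side.** One sentence of Section 10.10 stops collection below grade 2. Two other sentences of 10.10, and Sections 10.2.2 and 10.4.2 to 10.8.2, set no limit; the end-of-treatment visit, for example, says that the "relationship of each adverse event to therapy will be determined". They cannot all be followed for a grade 1 event.

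**2. Which DLT rows are exposed.** The graded rows of Table 9-2 start at grade 2 or higher, so their attribution is collected under either reading. A few clinical rows, such as a symptomatic cardiac event, state no grade. The row that expressly goes lower is the interruption row. It follows a row for intolerable grade 2 toxicity, so it covers tolerable grade 2 (attribution collected) and grade 1 (attribution not collected under the limit). The gap is grade 1 events in that row.

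**3. Whether the row can be reached.** Section 10.10.5 interrupts both drugs for suspected pneumonitis of any grade. The note in Table 10-2 lets the investigator omit BYL719 for any toxicity. Table 10-2 also counts omitted days from the decision and leaves the treatment calendar unchanged. If scheduled off-days count, an Arm C omission from day 7 to the next dosing day (day 15) covers days 7 to 14, which is 8 days. The documents do not say whether off-days count for this DLT row.

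**4. Size in the dose-finding phase.** The escalation probability in Section 14.2 is (1−p)³ + 3p(1−p)⁵.

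- p = 0.10: 0.729 + 0.177 = 0.906
- p = 0.20: 0.512 + 0.197 = 0.709
- p = 0.30: 0.343 + 0.151 = 0.494
- p = 0.40: 0.216 + 0.093 = 0.309

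These match the stated .91, .71, .49 and .31. If a share q of DLTs went uncounted, p becomes p(1−q). The documents give no value for q, so these are assumptions:

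| q | true 0.30 | true 0.40 |
|---|---|---|
| 0% | 0.494 | 0.309 |
| 10% | 0.557 | 0.378 |
| 25% | 0.654 | 0.494 |

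Only grade 1 events in one row are at issue, so q should lie near the top of this table.

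**5. The laboratory wording.** Boundaries of 2/5, 3/10, 4/15 and 5/20, evaluated by exact binomial recursion, give a stopping probability at a true 35% of 0.572 + 0.206 + 0.096 + 0.051 = 0.924 (unrounded terms), matching the stated .92. At 10% the same recursion gives 0.138 against the stated .10. That is a separate matter, and nothing here depends on it. If 10%, 25% or 50% of grade 4 toxicities were laboratory-only and left out (assumed shares), the probability at a true 35% would be 0.87, 0.74 or 0.42. Under the collection rule of Section 10.10 the share left out is 0%, and the probability stays at 0.92.

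**The case against.** The best defence is that attribution is judged in practice whatever the database field holds. Relationship is determined at the visits. The dose-modification guidance in Section 10.10.2 applies to toxicities considered at least possibly related, so a judgement comes before the action. The pneumonitis guidance itself turns on drug relationship. Toxicity is reviewed with the manufacturer at least monthly during dose finding. The Table 10-2 rows that list grade 1, and the grade 1 hyperglycemia and rash guidance, maintain the dose, so a grade 1 event that stops drug for more than a week would be unusual. Much of this stands: the event is likely rare, and it would be too strong to say that it cannot be classified. What remains is that the judgement need not be recorded, and the DLT count needs a record that can be checked.

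A reader might go further and infer that the DLT definition needs attribution at every grade. It does not; the exposure is the one row.

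A reader might also infer that Section 17.3 removes asymptomatic laboratory values from the DLT count and the stopping rule. The documents do not support that:

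- Section 9.4 names an abnormal laboratory value alongside an adverse event, and Table 9-2 lists asymptomatic lipase and amylase.
- Section 10.10 collects every laboratory toxicity of grade 2 or higher, and so every grade 4 one.
- The stopping rule counts grade 4 toxicity, not adverse events, and sets no attribution condition.
- The 17.3 sentence sits under SAE reporting and also admits values that require therapy.

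What is left of the laboratory question is a mismatch of wording.

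**Conclusion.** The point holds in a narrow form. Section 10.10 contradicts itself and the visit sections on attribution below grade 2, and the limit conflicts with the interruption row of Table 9-2. A grade 1 event meeting that row could lack the attribution needed to count it toward the primary endpoint. This rests on reading lower grade in that row as including grade 1, which its position after the grade 2 row supports.

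The number of affected events cannot be estimated from the documents and is probably very small. The consequence of a single one could still be a changed cohort decision. Section 1.0 reports accrual closed at 51 patients, so the amendment cannot alter enrolment decisions already taken. Its value now lies in confirming the DLT counts behind them. Undercounting is possible, not shown.

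The laboratory part is secondary: the texts should agree and the stopping rule should name its convention, but laboratory DLTs are already covered.

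**What to change.** - **Section 10.10:** amend the limiting sentence so that attribution is collected for adverse events of grade 2 or higher, and for any adverse event of any grade that leads to interruption, reduction or discontinuation of BYL719. Make the sentences before and after it, and the visit sections, agree. Section 9.4 interrupts drug for every DLT, so this also covers the rows without a stated grade.
- **Data check:** list Cycle 1 interruptions of BYL719 of more than 7 consecutive days, look for grade 1 events without attribution, and resolve them from source records. State whether scheduled off-days were counted.
- **Section 17.3:** align the laboratory sentence with 10.10, so that laboratory toxicities of grade 2 or higher are recorded whether or not symptomatic or treated.
- **Sections 9.6 and 14.3:** state that asymptomatic grade 4 laboratory values count as grade 4 toxicity in the global stopping rule.
- Say explicitly that DLT status stays governed by the grade and duration criteria of Table 9-2, so that recording a grade 2 laboratory value does not by itself make it a DLT.

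The cost is a few sentences, attribution fields for a small number of grade 1 events, and one data listing.
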